6.1 Study treatment

The investigational treatments for this study are asciminib (40 mg BID) and bosutinib (500 mg QD). Novartis will supply asciminib to the investigational site as 20 mg and 40 mg tablets. Bosutinib will be supplied to the investigational site as 100 mg and 500 mg tablets.

6.1.1 Dosing regimen

Asciminib

Asciminib 20 or 40 mg strength tablets will be administered orally twice-daily (BID), without food. Asciminib tablets should be ingested as follows:

- Asciminib should be administered in the fasted state: avoid food for at least 2 hours before the dose is taken and for at least 1 hour after the dose is taken. Water is permitted during this period.
 - Asciminib should be taken with approximately 8 ounces (240 mL) of water.
 - Asciminib should be swallowed whole and not chewed or crushed.
 - If vomiting occurs within the first hour after taking the drug, re-dosing is allowed before the next scheduled dose
- 

- If the patient does not take asciminib within 6 hours after the approximate time of the usual dosing time, that dose should be skipped and treatment should continue with the next daily dose at the prescribed level

Bosutinib

Bosutinib 500 mg or 100 mg tablets will be administered orally once daily (QD) with food. If a dose is missed beyond 12 hours, the patient should skip the dose and take the usual dose on the following day.

Table 6-1 Dose and treatment schedule

Study treatments	Pharmaceutical form and route of administration	Dose	Frequency and/or Regimen	Fasting Condition
Asciminib	Tablet for oral use	20 mg ^a	Twice-daily	Fasting
Asciminib	Tablet for oral use	40 mg	Twice-daily	Fasting
Bosutinib	Tablet for oral use	100 mg ^b	Once-daily	Non-fasting
Bosutinib	Tablet for oral use	500 mg	Once-daily	Non-fasting

^a 20 mg tablets will be dispensed to patients in the instance of dose reduction.

^b 100 mg tablets will be dispensed to patients in the instance of dose modifications.

On days when serial blood samples are collected for asciminib PK analysis, patients will be instructed to bring their drug supply to the site, and take the dose in the clinic, under supervision of the site personnel. The exact time for dose administration and meal intake must be recorded in the electronic Case Report Form (eCRF).

All dosages prescribed and dispensed to the patient and all dose changes during the study must be recorded on the Dosage Administration Record eCRF.

6.1.2 Ancillary treatments

Not applicable.

6.1.3 Rescue medication

Not applicable.

6.1.4 Guidelines for continuation of treatment

Not applicable. See [Section 6.3](#).

6.1.5 Treatment duration

There is no fixed duration of treatment planned per patient. The patients are treated in the study up to end of study treatment period defined as up to 96 weeks after the last patient receives the first dose or up to 48 weeks after the last patient has switched to asciminib treatment whichever is longer unless patients have discontinued treatment earlier. Patients may be discontinued from treatment with the study drug at any time due to unacceptable toxicity, disease progression and/or at the discretion of the investigator or the patient.

6.2 Dose escalation guidelines

Dose escalation beyond the standard doses of 40 mg BID for asciminib is not permitted.

Dose escalation above 500 mg QD for bosutinib is permitted in this study. Bosutinib escalation guidelines are as follows:

Consider dose escalation to 600 mg once daily in patients who are currently taking 500 mg daily, did not have Grade 3 or higher adverse events and who:

- Did not reach complete hematological response (CHR) by week 8
- Did not reach complete cytogenetic response (CCyR) by week 12

6.3 Dose modifications

6.3.1 Dose modification and dose delay

[figure not shown]
For patients who do not tolerate the protocol-specified dosing schedule, dose interruptions and/or reductions are either recommended or mandated in order to allow the patient to continue the study treatment.

These dose modifications are summarized in [Table 6-2](#). The dose reduction indicated as “recommendations” are provided to assist investigators in the event the patient experiences toxicity. However, deviations from “mandatory” dose interruptions and/or reductions are not allowed and mandatory interruptions or reductions must be strictly followed. Re-escalation to asciminib 40 mg BID is permitted if a change in the patient’s individual benefit/risk assessment at the lower dose level is seen. Re-escalation will be allowed only once for any given patient on the asciminib arm per protocol. Permanent treatment discontinuation is mandatory for specific events indicated as such in [Table 6-2](#). Any dose changes must be recorded on the Dosage Administration Record eCRF.

[figure not shown]
A patient must discontinue treatment with either asciminib or bosutinib if, after treatment is resumed at a lower dose level, the toxicity recurs with the same or worse severity, except for recurrence of cytopenias ([Table 6-2](#)). If a patient requires a dose interruption of > 28 days for each non-hematologic toxicity, then the patient must be discontinued from the study treatment. If a hematologic toxicity (cytopenia Grade 3 or 4) lasts for more than 42 days without recovery to at least a Grade 2, despite TKI interruption and adequate management (including hematopoietic growth factors), then the patient must be discontinued from the study treatment.

Table 6-2 Criteria for dose reduction/interruption and re-initiation of asciminib and bosutinib treatment for adverse drug reactions

[figure not shown]
Dose modifications for both asciminib and bosutinib		
Please note that if a patient requires a dose interruption of > 28 days for each toxicity, then the patient must be discontinued from the study treatment		
Worst toxicity CTCAE Grade 4.03	Asciminib	Bosutinib
Investigations (Hematologic) If a hematologic toxicity (cytopenia Grade 3 or 4) lasts for more than 42 days without recovery to at least a Grade 2, despite TKI interruption and adequate management (including hematopoietic growth factors), then the patient must be discontinued from the study treatment.		
Neutropenia (ANC)		
Grade 1 (ANC < LLN – 1.5 x 10 ⁹ /L)	Recommendation: Maintain dose level	Recommendation: Maintain dose level
Grade 2 (ANC < 1.5 – 1.0 x 10 ⁹ /L)	Recommendation: Maintain dose level	Recommendation: Maintain dose level
Grade 3 (ANC < 1.0 – 0.5 x 10 ⁹ /L)	Mandatory: Hold dose until resolved to ≤ Grade 2 (recheck CBC 2x/week), then: if resolved in ≤ 14 days, then maintain dose level If resolved in > 14 days, then reduce dose ↓ 1 dose level	Mandatory: Hold dose until resolved to ≤ Grade 2 and platelets ≤ Grade 2 (recheck CBC 2x/week), then: if resolved in ≤ 14 days, then maintain dose level If resolved in > 14 days, reduce dose ↓ 1 dose level
Grade 4 (ANC < 0.5 x 10 ⁹ /L)	Mandatory: Hold dose until resolved to ≤ Grade 2, (recheck CBC 2x/week), then: if resolved in ≤ 14 days, then maintain dose level if resolved in > 14 days, then reduce dose ↓ 1 dose level	Mandatory: Hold dose until resolved to ≤ Grade 2 and platelets ≤ Grade 2 (recheck CBC 2x/week), then: if resolved in ≤ 14 days, then maintain dose level if resolved in > 14 days, then reduce dose ↓ 1 dose level
Febrile neutropenia (ANC < 1.0 x 10 ⁹ /L, fever ≥ 38.5°C)	Mandatory: Hold dose until resolved, then reduce dose ↓ 1 dose level	Mandatory: Hold dose until resolved, then reduce dose ↓ 1 dose level
Thrombocytopenia		
Grade 1 (PLT < LLN – 75 X 10 ⁹ /L)	Recommendation: Maintain dose level	Recommendation: Maintain dose level
Grade 2 (PLT < 75 - 50 x 10 ⁹ /L)	Recommendation: Maintain dose level	Recommendation: Maintain dose level

[figure not shown]
Dose modifications for both asciminib and bosutinib		
Please note that if a patient requires a dose interruption of > 28 days for each toxicity, then the patient must be discontinued from the study treatment		
Worst toxicity CTCAE Grade 4.03	Asciminib	Bosutinib
Grade 3 (PLT < 50 - 25 x 10 ⁹ /L)	Mandatory: Hold dose until resolved to ≤ Grade 2 (recheck CBC 2x/week), then: if resolved in ≤ 14 days, then maintain dose level if resolved in > 14 days, then reduce dose ↓ 1 dose level	Mandatory: Hold dose until resolved to ≤ Grade 2 and neutrophils ≤ Grade 2 (recheck CBC 2x/week), then: if resolved in ≤ 14 days, then maintain dose level if resolved in > 14 days, then reduce dose ↓ 1 dose level
Grade 4 (PLT < 25 x 10 ⁹ /L)	Mandatory: Hold dose until resolved to ≤ Grade 2 (recheck CBC 2x/week), then: if resolved in ≤ 14 days, then maintain dose level if resolved in > 14 days, then reduce dose ↓ 1 dose level	Mandatory: Hold dose until resolved to ≤ Grade 2 and neutrophils ≤ Grade 2 (recheck CBC 2x/week), then: if resolved in ≤ 14 days, then maintain dose level if resolved in > 14 days, then reduce dose ↓ 1 dose level
Recurrence of all cytopenias	Recommendation: Hold dose until resolved to ≤ Grade 2, then maintain current dose level.	Recommendation: Hold dose until resolved to ≤ Grade 2, then reduce dose ↓ 1 additional level
Non-hematologic adverse reactions except where further specified in individual sections		
Grade 1	Recommendation: Maintain dose level	Recommendation: Maintain dose level
Grade 2	Recommendation: Hold dose until resolved to ≤ Grade 1, then maintain dose level	Recommendation: Maintain dose level
Grade 3	Mandatory: Hold dose until resolved to ≤ Grade 1, then reduce dose ↓ 1 dose level	Mandatory: Hold dose until resolved to ≤ Grade 1, then reduce dose ↓ 1 dose level, If clinically appropriate, re-escalation of the dose back to baseline dose level (500 mg) should be considered
Grade 4	Mandatory: Permanently discontinue patient from study drug treatment.	Mandatory: Hold dose until resolved to ≤ Grade 1, then reduce dose ↓ 1 dose level; If clinically appropriate, re-escalation of the dose back to baseline dose level (500 mg) should be considered
Investigations (Renal)		
Serum creatinine		
Grade 1 (> ULN - 1.5 x ULN)	Recommendation: Maintain dose level	Recommendation: Maintain dose level
Grade 2 (> 1.5 - 3.0 x ULN)	Recommendation: Hold dose until resolved to ≤ Grade 1 or baseline, then maintain dose level	Recommendation: Hold dose until resolved to ≤ Grade 1 or baseline, then maintain dose level
Grade 3 (> 3.0 - 6.0 x ULN)	Mandatory: Permanently discontinue patient from study drug treatment.	Mandatory: Permanently discontinue patient from study drug treatment.
Grade 4 (> 6.0 x ULN)	Mandatory: Permanently discontinue patient from study drug treatment.	Mandatory: Permanently discontinue patient from study drug treatment.

[figure not shown]
Dose modifications for both asciminib and bosutinib		
Please note that if a patient requires a dose interruption of > 28 days for each toxicity, then the patient must be discontinued from the study treatment		
Worst toxicity CTCAE Grade 4.03	Asciminib	Bosutinib
Investigations (Hepatic)		
Isolated total Bilirubin elevation		
> ULN – 1.5 x ULN	Recommendation: Maintain dose level	Recommendation: Maintain dose level
> 1.5 - 3.0 x ULN	Recommendation: Hold dose. Monitor LFTs ^b weekly, or more frequently if clinically indicated, until resolved to ≤ 1.5 x ULN: if resolved in ≤ 14 days, then maintain dose level if resolved in > 14 days, then reduce dose ↓ 1 dose level	Recommendation: Hold dose. Monitor LFTs ^b weekly, or more frequently if clinically indicated, until resolved to ≤ 1.5 x ULN: if resolved in ≤ 14 days, then maintain dose level if resolved in > 14 days, then reduce dose ↓ 1 dose level
> 3.0 - 10.0 x ULN*	Mandatory: Hold dose. Monitor LFTs ^b weekly, or more frequently if clinically indicated, until resolved to ≤ 1.5 x ULN: if resolved in ≤ 14 days, then reduce dose ↓ 1 dose level if resolved in > 14 days, then discontinue patient from study drug treatment. The patient should be monitored weekly (including LFTs ^b), or more frequently if clinically indicated, until total bilirubin have resolved to baseline or stabilization over 4 weeks.	Mandatory: Hold dose. Monitor LFTs ^b weekly, or more frequently if clinically indicated, until resolved to ≤ 1.5 x ULN: if resolved in ≤ 14 days, then reduce dose ↓ 1 dose level if resolved in > 14 days, then discontinue patient from study drug treatment. The patient should be monitored weekly (including LFTs ^b), or more frequently if clinically indicated, until total bilirubin have resolved to baseline or stabilization over 4 weeks.
> 10.0 x ULN*	Mandatory: Permanently discontinue patient from study drug treatment. The patient should be monitored weekly (including LFTs ^b), or more frequently if clinically indicated, until total bilirubin have resolved to baseline or stabilization over 4 weeks.	Mandatory: Permanently discontinue patient from study drug treatment. The patient should be monitored weekly (including LFTs ^b), or more frequently if clinically indicated, until total bilirubin have resolved to baseline or stabilization over 4 weeks.
Isolated AST or ALT elevation		
> ULN - 3.0 x ULN	Recommendation: Maintain dose level	Recommendation: Maintain dose level
> 3.0 - 5.0 x ULN	Recommendation: Maintain dose level. Repeat LFTs ^b as soon as possible, preferably within 48-72 hours from awareness of the abnormal results; if abnormal lab values are confirmed upon the repeat test, then monitor LFTs ^b weekly, or more frequently if clinically indicated, until resolved to ≤ 3.0 x ULN	Recommendation: Maintain dose level. Repeat LFTs ^b as soon as possible, preferably within 48-72 hours from awareness of the abnormal results; if abnormal lab values are confirmed upon the repeat test, then monitor LFTs ^b weekly, or more frequently if clinically indicated, until resolved to ≤ 3.0 x ULN

[figure not shown]
Dose modifications for both asciminib and bosutinib Please note that if a patient requires a dose interruption of > 28 days for each toxicity, then the patient must be discontinued from the study treatment		
Worst toxicity CTCAE Grade 4.03	Asciminib	Bosutinib
> 5.0 - 10.0 x ULN	Mandatory: Hold dose. Repeat LFTs ^b as soon as possible, preferably within 48-72 hours from awareness of the abnormal results; monitor LFTs ^b weekly, or more frequently if clinically indicated, until resolved to ≤ 3.0 x ULN: Then If resolved in ≤ 14 days, maintain dose level If resolved in > 14 days, reduce dose ↓ 1 dose level	Mandatory: Hold dose. Repeat LFTs ^b as soon as possible, preferably within 48-72 hours from awareness of the abnormal results; monitor LFTs ^b weekly, or more frequently if clinically indicated, until resolved to ≤ 2.5 x ULN: Then Recommendation: If resolved in ≤ 28 days, reduce dose ↓ 1 dose level Recommendation: If resolved in > 28 days, Discontinue patient from study drug treatment
> 10.0 - 20.0 x ULN	Mandatory: Hold dose. Repeat LFTs ^b as soon as possible, preferably within 48-72 hours from awareness of the abnormal results; monitor LFTs ^b weekly, or more frequently if clinically indicated, until resolved to ≤ baseline. Then reduce dose ↓ 1 dose level.	Mandatory: Hold dose. Repeat LFTs ^b as soon as possible, preferably within 48-72 hours from awareness of the abnormal results; monitor LFTs ^b weekly, or more frequently if clinically indicated, until resolved to ≤ 2.5 x ULN. Then Recommendation: If resolved in ≤ 28 days, reduce dose ↓ 1 dose level maintain dose level Recommendation: If resolved in > 28 days, Discontinue patient from study drug treatment.
> 20.0 x ULN	Mandatory: Hold dose. Repeat LFTs ^b as soon as possible, preferably within 48-72 hours from awareness of the abnormal results; monitor LFTs ^b weekly, or more frequently if clinically indicated, until resolved to ≤ 3 x ULN (or ≤ 5 x ULN for patients with baseline value > 3.0 -5.0 x ULN), then resume treatment at reduce dose ↓ 1 dose level. Only 1 dose reduction is allowed; if reoccurs at > 5 x ULN, discontinue patient from study drug treatment.	Mandatory: Hold dose. Repeat LFTs ^b as soon as possible, preferably within 48-72 hours from awareness of the abnormal results; monitor LFTs ^b weekly, or more frequently if clinically indicated, until resolved to ≤ 2.5 x ULN (then Recommendation: If resolved in ≤ 28 days, reduce dose ↓ 1 dose level maintain dose level Recommendation: If resolved in > 28 days, Discontinue patient from study drug treatment

[figure not shown]
Dose modifications for both asciminib and bosutinib Please note that if a patient requires a dose interruption of > 28 days for each toxicity, then the patient must be discontinued from the study treatment		
Worst toxicity CTCAE Grade 4.03	Asciminib	Bosutinib
Combined ^c elevations of AST or ALT and total bilirubin		
For patients with normal baseline ALT and AST and total bilirubin value: AST or ALT >3.0 x ULN combined with total bilirubin >2.0 x ULN without evidence of cholestasis ^d For patients with elevated baseline AST or ALT or total bilirubin value [AST or ALT >2 x baseline AND > 3.0 x ULN]	Mandatory: Permanently discontinue patient from study drug treatment. Repeat as soon as possible, preferably within 48 hours from awareness of the abnormal results, then with weekly monitoring of LFTs ^b), or more frequently if clinically indicated, until AST, ALT, or bilirubin have resolved to baseline or stabilization over 4 weeks. Refer to Section 6.3.3.1 for additional follow-up evaluations as applicable.	Mandatory: Permanently discontinue patient from study drug treatment. Repeat as soon as possible, preferably within 48 hours from awareness of the abnormal results, then with weekly monitoring of LFTs ^b), or more frequently if clinically indicated, until AST, ALT, or bilirubin have resolved to baseline or stabilization over 4 weeks. Refer to Section 6.3.3.1 for additional follow-up evaluations as applicable.
Investigation (metabolic)		
Asymptomatic amylase and/or lipase elevation		
Grade 1 (> ULN - 1.5 x ULN)	Recommendation: Maintain dose level, measure 2x week	Recommendation: Maintain dose level, measure 2x week
Grade 2 (> 1.5 - 2.0 x ULN)	Recommendation: Maintain dose level, measure 2x week	Recommendation: Maintain dose level, measure 2x week
Grade 3 (> 2.0 - 5.0 x ULN)	Mandatory: Hold dose until resolved to Grade ≤ 1 or baseline, then: If resolved in ≤ 7 days, then reduce dose ↓ 1 dose level If resolved in > 7 days, then discontinue treatment and obtain appropriate imaging (i.e., MRI, CT scan or ultrasound).	Mandatory: Hold dose until resolved to Grade ≤ 1 or baseline, then: If resolved in ≤ 7 days, then reduce dose ↓ 1 dose level If resolved in > 7 days, then discontinue treatment and obtain appropriate imaging (i.e., MRI, CT scan or ultrasound).
Grade 4 (> 5.0 x ULN)	Mandatory: Permanently discontinue patient from study drug treatment. Obtain appropriate imaging (i.e., MRI, CT scan or ultrasound).	Mandatory: Permanently discontinue patient from study drug treatment. Obtain appropriate imaging (i.e., MRI, CT scan or ultrasound).

Dose modifications for both asciminib and bosutinib		
Please note that if a patient requires a dose interruption of > 28 days for each toxicity, then the patient must be discontinued from the study treatment		
Worst toxicity CTCAE Grade 4.03	Asciminib	Bosutinib
Vascular disorders		
Hypertension		
CTCAE Grade 3	Mandatory: Hold dose until resolved \leq Grade 1, then reduce dose \downarrow 1 dose level	Mandatory: Hold dose until resolved \leq Grade 1, then reduce dose \downarrow 1 dose level
CTCAE Grade 4	Mandatory: Permanently discontinue patient from study drug treatment.	Mandatory: Permanently discontinue patient from study drug treatment.
Gastro intestinal		
Pancreatitis		
Grade 2 (radiologic findings for pancreatitis as per CTCAE v4.03, for increased enzymes please see table for asymptomatic amylase and/or lipase elevation)	Mandatory: If asymptomatic radiologic pancreatitis, hold treatment until recovery of the radiologic findings. If treatment delay is \leq 21 days, then reduce dose \downarrow 1 dose level. If treatment delay > 21 days, discontinue treatment and keep monitoring with appropriate imaging (i.e., MRI, CT scan or ultrasound).	Mandatory: If asymptomatic radiologic pancreatitis, hold treatment until recovery of the radiologic findings. If treatment delay is \leq 21 days, then reduce dose \downarrow 1 dose level. If treatment delay > 21 days, discontinue treatment and keep monitoring with appropriate imaging (i.e., MRI, CT scan or ultrasound).
Grade \geq 3	Mandatory: Permanently discontinue patient from study drug treatment. Obtain appropriate imaging (i.e., MRI, CT scan or ultrasound).	Mandatory: Permanently discontinue patient from study drug treatment. Obtain appropriate imaging (i.e., MRI, CT scan or ultrasound).
Diarrhea***		
Grade 1	Recommendation: Maintain dose level but, initiate anti-diarrhea treatment	Recommendation: Maintain dose level but, initiate anti-diarrhea treatment
Grade 2	Recommendation: Hold dose until resolved to \leq grade 1, then maintain dose level. If diarrhea returns as \geq grade 2, then hold dose until resolved to \leq grade 1, then reduce dose \downarrow 1 dose level	Recommendation: Hold dose until resolved to \leq grade 1, then maintain dose level. If diarrhea returns as \geq grade 2, then hold dose until resolved to \leq grade 1, then reduce dose \downarrow 1 dose level
Grade 3	Recommendation: Hold dose and discontinue patient from study drug treatment	Mandatory: Hold dose until recovery to \leq grade 1. Recommendation: Bosutinib may then be resumed at \downarrow 1 dose level
Grade 4	Mandatory: Permanently discontinue patient from study drug treatment	Mandatory: Hold dose until recovery to \leq grade 1. Recommendation: Bosutinib may then be resumed at \downarrow 1 dose level

Dose modifications for both asciminib and bosutinib		
Please note that if a patient requires a dose interruption of > 28 days for each toxicity, then the patient must be discontinued from the study treatment		
Worst toxicity CTCAE Grade 4.03	Asciminib	Bosutinib
Skin and subcutaneous tissue disorders		
Rash/photosensitivity		
Grade 1	Recommendation: Maintain dose level. Consider to initiate appropriate skin toxicity therapy (such as antihistamines, topical corticosteroids and low-dose systemic corticosteroids)	Recommendation: Maintain dose level. Consider to initiate appropriate skin toxicity therapy (such as antihistamines, topical corticosteroids and low-dose systemic corticosteroids)
Grade 2	Recommendation: Maintain dose level, but initiate/intensify appropriate skin toxicity therapy (such as antihistamines, topical corticosteroids and low-dose systemic corticosteroids)	Recommendation: Maintain dose level, but initiate/intensify appropriate skin toxicity therapy (such as antihistamines, topical corticosteroids and low-dose systemic corticosteroids)
Grade 3, despite skin toxicity therapy	Recommendation: Hold dose until resolved to Grade ≤ 1, then: If resolved in ≤ 7 days, then reduce dose ↓ 1 dose level If resolved in > 7 days (despite appropriate skin toxicity therapy), then discontinue patient from study drug treatment	Recommendation: Hold dose until resolved to Grade ≤ 1, then: If resolved in ≤ 7 days, then reduce dose ↓ 1 dose level If resolved in > 7 days (despite appropriate skin toxicity therapy), then discontinue patient from study drug treatment
Grade 4, despite skin toxicity therapy	Mandatory: Permanently discontinue patient from study drug treatment.	Mandatory: Permanently discontinue patient from study drug treatment.
General disorders and administration site conditions		
Fatigue/ Asthenia		
Grade 1 or 2	Recommendation: Maintain dose level	Recommendation: Maintain dose level
Grade 3	Recommendation: Hold dose until resolved to ≤ grade 1, then : If resolved in ≤ 7 days, then maintain dose level If resolved in > 7 days, then reduce dose ↓ 1 dose level	Recommendation: Hold dose until resolved to ≤ grade 1, then : If resolved in ≤ 7 days, then maintain dose level If resolved in > 7 days, then reduce dose ↓ 1 dose level
All dose modifications should be based on the worst preceding toxicity.		
^a Common Toxicity Criteria for Adverse Events (CTCAE Version 4.03)		
^b Core LFTs consist of ALT, AST, total bilirubin (fractionated [direct and indirect], if total bilirubin > 2.0 x ULN), and alkaline phosphatase (fractionated [quantification of isoforms], if alkaline phosphatase > 2.0 x ULN.)		
^c “Combined” defined as total bilirubin increase to the defined threshold concurrently with ALT/AST increase to the defined threshold		

Dose modifications for both asciminib and bosutinib		
Please note that if a patient requires a dose interruption of > 28 days for each toxicity, then the patient must be discontinued from the study treatment		
Worst toxicity CTCAE Grade 4.03	Asciminib	Bosutinib

If combined elevations of AST or ALT and total bilirubin do not meet the defined thresholds, please follow the instructions for isolated elevation of total bilirubin and isolated elevation of AST/ALT, and take a conservative action based on the degree of the elevations (e.g. discontinue treatment at the situation when hold dose is needed for one parameter and discontinue treatment is required for another parameter). After all elevations resolve to the defined thresholds that allow treatment re-initiation, re-start the treatment either at the same dose or at one dose lower if meeting a criterion for dose reduction
 
^d “Cholestasis” defined as ALP elevation (>2.0 x ULN and R value <2) in patients without bone metastasis, or elevation of ALP liver fraction in patients with bone metastasis
 
Note: The R value is calculated by dividing the ALT by the ALP, using multiples of the ULN for both values. It denotes whether the relative pattern of ALT and/or ALP elevation is due to cholestatic (R ≤ 2), hepatocellular (R ≥ 5), or mixed (R >2 and < 5) liver injury
 
* Note: If total bilirubin > 3.0 x ULN is due to the indirect (non-conjugated) component only, and hemolysis as the etiology has been ruled out as per institutional guidelines (e.g., review of peripheral blood smear and haptoglobin determination), then ↓ 1 dose level and continue treatment at the discretion of the investigator.
 
** Note: A CT scan or other imaging study to assess the pancreas, liver, and gallbladder must be performed within 1 week of the first occurrence of any ≥ Grade 3 of amylase and/or lipase. If asymptomatic Grade 2 elevations of lipase and/or amylase occur again at the reduced dose, patients will be discontinued permanently from study treatment.
 
*** Note: antidiarrheal medication is recommended at the first sign of abdominal cramping, loose stools or overt diarrhea
		

[figure not shown]

Table 6-3 Dose reduction steps for asciminib and bosutinib

Dose reduction*			
	Starting dose level – 0	Dose level – 1	
Asciminib BID	40 mg tablet BID (total daily dose 80 mg)	20 mg tablet BID (total daily dose 40 mg)	
*Dose reduction should be based on the worst toxicity demonstrated at the last dose.			
Asciminib dose reduction below total daily 40 mg is not allowed. 20 mg tablets will be dispensed to patients in the instance of dose reduction.			
Dose reduction*			
	Starting dose level – 0	Dose level – 1	Dose level – 2
Bosutinib QD	500 mg (1-500 mg tablet QD)	400 mg (4-100 mg tablets QD)	300 mg (3-100 mg tablets QD)
* Dose reduction should be based on the worst toxicity demonstrated at the last dose.			
Bosutinib dose reduction below total daily 300 mg is not allowed. 100 mg tablets will be dispensed to patients in the instance of dose reduction.			

[figure not shown]

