6.3 Dose modifications

6.3.1 Dose modification and dose delay

For patients who do not tolerate the protocol-specified dosing schedule, dose interruptions and/or reductions are either recommended or mandated in order to allow the patient to continue the study treatment.

[figure not shown]
These dose modifications are summarized in [Table 6-2](#). The dose reduction indicated as “recommendations” are provided to assist investigators in the event the patient experiences toxicity. However, deviations from “mandatory” dose interruptions and/or reductions are not

allowed and mandatory interruptions or reductions must be strictly followed. Re-escalation to ABL001 40mg BID is permitted if a change in the patient's individual benefit/risk assessment at the lower dose level is seen. Re-escalation will be allowed only once for any given patient on the ABL001 arm per protocol. Permanent treatment discontinuation is mandatory for specific events indicated as such in [Table 6-2](#). Any dose changes must be recorded on the Dosage Administration Record eCRF.

[figure not shown]
A patient must discontinue treatment with either ABL001 or bosutinib if, after treatment is resumed at a lower dose, the toxicity recurs with the same or worse severity (See [Table 6-2](#)). If a patient requires a dose interruption of > 28 days, then the patient must be discontinued from the study treatment. Patients who discontinue the study treatment for an adverse event suspected to be related to study drug or an abnormal laboratory value suspected to be related to study drug must be followed as described in [Section 8](#).

Table 6-2 Criteria for dose reduction/interruption and re-initiation of ABL001 and bosutinib treatment for adverse drug reactions

[figure not shown]
Dose modifications for both ABL001 and bosutinib		
Worst toxicity CTCAE Grade 4.03	ABL001	bosutinib
Investigations (Hematologic)		
Neutropenia (ANC)		
Grade 1 (ANC < LLN – 1.5 x 10 ⁹ /L)	Recommendation: Maintain dose level	Recommendation: Maintain dose level
Grade 2 (ANC < 1.5 – 1.0 x 10 ⁹ /L)	Recommendation: Maintain dose level	Recommendation: Maintain dose level

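### The Amendment 3 Table 6-2 header applies the 28-day stop to every toxicity, while Section 6.3.1 and the table's own sub-heading allow Grade 3/4 cytopenia 42 days

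*Combined protocol and SAP*

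**What the plan says.** All of the conflicting text is current Amendment 3 text, in Section 6.3.1 and the table it introduces.

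- **Section 6.3.1, body text, non-hematologic.** The 28-day stop is limited by class: "If a patient requires a dose interruption of > 28 days for each non-hematologic toxicity", the patient must come off study treatment.
- **Section 6.3.1, body text, hematologic.** A separate limit applies: "If a hematologic toxicity (cytopenia Grade 3 or 4) lasts for more than 42 days without recovery to at least a Grade 2", despite interruption and adequate management, the patient must come off study treatment. The hematologic sub-heading inside Table 6-2 repeats this rule.
- **Table 6-2, header.** The header row tells sites that "if a patient requires a dose interruption of > 28 days for each toxicity, then the patient must be discontinued from the study treatment". It is printed eight times, once at the start and again on each continuation of the table. No printing carries an exception for cytopenia.
- **Table 6-2, hematologic rows.** Six rows tell the site to hold the dose, in both arms: neutropenia Grade 3 and Grade 4, febrile neutropenia, thrombocytopenia Grade 3 and Grade 4, and "Recurrence of all cytopenias". The first five are mandatory holds; the last is a recommendation. The febrile neutropenia row, for example, says "Mandatory: Hold dose until resolved, then reduce dose" by one level. None of the six sets a maximum length for the hold.

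**The concern.** The header and the text it should summarise give different stopping limits for the same event. Investigators use Table 6-2 at the point of decision, and the header is phrased as an obligation.

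The layout makes a literal reading easier. The 42-day sub-heading appears once in the table, above the neutropenia rows. The header is printed again directly above the Grade 3 platelet row. From there through the Grade 4 platelet and recurrence rows, 28 days is the only overall limit on the page.

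At stake is whether a patient with slow hematologic recovery is permanently withdrawn from study treatment although Section 6.3.1 would keep that patient on it. Sites could also handle identical patients differently: one following the header stops treatment, while one following Section 6.3.1 departs from a mandatory-sounding line in the table.

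**Working it through.** The plan gives no figure to reproduce, so the check compares the rules and then finds where they disagree.

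**Step 1. The rules side by side (Amendment 3).**

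| Source | Applies to | Limit | What is counted |
|---|---|---|---|
| Table 6-2 header | each toxicity | more than 28 days | days of dose interruption |
| Section 6.3.1 body | each non-hematologic toxicity | more than 28 days | days of dose interruption |
| Section 6.3.1 body and Table 6-2 hematologic sub-heading | Grade 3 or 4 cytopenia | more than 42 days without recovery to Grade 2 | days of toxicity |

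For non-hematologic toxicity the header and the body agree. For Grade 3/4 cytopenia they do not.

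**Step 2. Do the two clocks measure the same thing?** Not exactly: one counts interruption, the other counts toxicity. The mandatory hold ties them together, because the dose stays off until the cytopenia resolves. They differ only by any delay between onset and the start of the hold.

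**Step 3. The conflict window.** Let R be the day of recovery to Grade 2 or lower, counted from onset, and d the days from onset to the start of the hold. The plan gives no value for d, so it is an assumption shown over a range.

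- The header stops the patient if R − d > 28, that is, R > 28 + d.
- Section 6.3.1 stops the patient only if R > 42.
- The rules conflict when 28 + d < R ≤ 42, a window of 42 − (28 + d) = 14 − d days.

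| d (assumed) | Recovery days in conflict | Window |
|---|---|---|
| 0 | 29 to 42 | 14 days |
| 3 | 32 to 42 | 11 days |
| 7 | 36 to 42 | 7 days |
| 14 or more | none | 0 days |

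Below the window neither rule requires a stop. Above day 42, Section 6.3.1 requires one.

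**Step 4. Which rule is intended?** The Amendment 3 rationale and summary of changes, used here only as evidence of intent, say that the recovery period for cytopenia was lengthened from 28 to 42 days. Section 6.3.1 and the sub-heading carry that change; the header does not. In the Amendment 1 protocol, the Section 6.3.1 body had a single rule for all toxicities: "If a patient requires a dose interruption of > 28 days, then the patient must be discontinued from the study treatment". None of the eight table headers in that version carried it. The Amendment 3 header thus states the broader rule that the body text has since narrowed.

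**The case against.** The best defence is that the document resolves the conflict itself. Section 6.3.1 states both limits just before the table. The first sub-heading under the first header is the hematologic one, and it gives the 42-day limit in equally mandatory terms. A specific rule is ordinarily read as governing over a general note, so a careful investigator would apply 42 days. This stands, and it is why the point is no more than minor to moderate. It does not make the header correct: the header has no wording that yields to a more specific rule, and the sub-heading is not repeated where the header is.

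A reader might infer that the header overrides the body text, because Section 6.3.1 says "Permanent treatment discontinuation is mandatory for specific events indicated as such in" Table 6-2. The documents do not support that. The sentence concerns named events, which fits rows such as Grade 3 or 4 creatinine that are marked as mandatory permanent stops. The header names no event, opens as a note and has no mandatory label. It is an instruction a site could follow, not a rule that displaces Section 6.3.1.

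It is also fair to say that the header's history is unknown. It is absent from the Amendment 1 table, and the full Amendment 2 text is not in the documents, so when it was added cannot be established. The inconsistency does not depend on that.

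**Conclusion.** The point holds as an internal inconsistency. The Table 6-2 header is wrong as written for Grade 3/4 cytopenia, and Section 6.3.1 and the hematologic sub-heading state the intended rule. Read literally, the header would permanently stop a patient who recovers between about day 29 and day 42. That window assumes the hold starts at onset and ends at recovery, and it shrinks by one day for each day the hold is delayed.

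Three stronger readings are tempting, and the documents do not carry them.

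- **An effect on the Week 24 response rate.** Section 10.4.3 of the Amendment 1 protocol counts stopping before 24 weeks as non-response, so a reader might infer bias in the primary endpoint. The corresponding Amendment 3 section is not in the documents reviewed, and nothing shows how many patients in either arm would fall in the window. No endpoint effect is claimed.
- **An estimate of the number affected.** Section 1.2.1.2 lists thrombocytopenia and neutropenia among the common phase 1 adverse events at 40 mg BID, but without grade or duration. It says nothing about Grade 3/4 cytopenia lasting 29 to 42 days, so the number cannot be estimated.
- **Patients left without options.** The Amendment 3 remark that patients may lack alternatives outside the trial belongs to the rationale for repeat screening, not to the cytopenia change. It cannot be used to weigh this point.

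**What to change.** In the Table 6-2 header, insert the word non-hematologic before toxicity in all eight printings, so that it matches Section 6.3.1. Make the change in the next protocol amendment and send sites a clarification that the 42-day limit governs Grade 3/4 cytopenia.

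The cost is one word in a repeating row, with no new clinical decision and no change to data collection or analysis. It is still a protocol change. Section 12.1 of the Amendment 1 protocol requires a written amendment with sponsor and ethics committee approval, and health authority approval where required; the Amendment 3 contents list the same section. Bundling it with the next amendment avoids a separate round.

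Two nearby items could be tidied at the same time. They are optional and not part of this point.

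- The elevated-baseline line of the combined liver row shows only the transaminase criterion. The row title and its footnote already require bilirubin, and Section 6.3.3.1, which the row cites, gives the full thresholds.
- Two bosutinib cells for isolated transaminase elevation follow a dose reduction with stray words about maintaining the dose. They concern only a recommended restart dose, and the text may have been damaged in extraction.
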